and STS, fewer randomized trials have studied the effect of care coordination on post-discharge outcomes of cardiac patients. These studies found conflicting results on the effectiveness of care coordination, in part due to variation in institutional context as well as the types of intervention provided (Peikes et al, 2009; Harrison et al.,2002; Naylor et al, 2004). In all, the available evidence suggests that the two main features of CareHub are likely to result in positive changes to patient outcomes as well as reductions in resource utilisation.

Design

Inclusion and Exclusion Criteria and Consenting

The sample will include all cardiac patients who are eligible for CareHub, and were admitted to Wards 63 / 64 (post-cardiac surgery recovery wards) at NUH during the CareHub pilot. Recruitment for this pilot will be from 20 April 2016 – end November 2016, and the CareHub team will provide 6 months of post-discharge support.

All patients meeting a pre-defined minimum LACE score will be enrolled into the program and randomly assigned to CareHub or Usual Care (the existing package of post-discharge care services). All patients between 18 and 99 years of age will be included. Patients below 18 years of age will be excluded. Patients that do not consent or are unable to consent to the program will be excluded.

We will aim for a balanced design, as far as possible, in which the number of patients in the Usual Care and CareHub groups will be equal.

Written informed consent will be sought from patients admitted to Wards 63 /64 by a ward nurse that is not part of the study team. Request for informed consent will be delivered in the primary language of the patient (English, Mandarin Chinese or dialect, Malay or Tamil).

Individuals who agree to participate in the survey will be eligible for a lottery consisting of 10 prizes of \$10 each. The lottery will take place in May 2017. Winners will be informed by phone and the prize will be mailed to them. The lottery is meant as partial compensation for participants' time spent answering the survey. We choose the lottery, rather than a guaranteed sum due to budget constraints. The amount of the lottery is set at the low amount of \$10 to avoid undue influence of patients' decisions regarding survey participation.

Sample size

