NUHS estimates that the total size of the population during the 6 month period to be approximately 1000 patients, of which 250 will be enrolled in CareHub, with a corresponding 250 in the control group. For the survey, due to resource constraints, we aim to randomly survey a total of 400 pairs of patients and their caregivers. 200 from CareHub and the rest from the control group.

The control group is anticipated to be a robust control because NUH randomly allocates the pool of eligible patients into CareHub and existing care. Table 1 summarizes the minimum detectable standardized effect size (MDE) for outcomes measured by the survey based on a 5% (2-sided) Type 1 error rate, different survey response rates, and different levels of statistical power for survey respondents. The MDE for outcomes captured by hospital administrative data will be lower (i.e. better) than those in the 100% response column, because administrative data are available for a larger group of patients.

Table 1

Total no. of patients in the CareHub and non- CareHub groups responding to the survey (response rate)	400 (100%)	300 (75%)	200 (50%)	120 (30%)
	Minimum detectable effect sizes			
80% power	0.28	0.32	0.40	0.52
90% power	0.32	0.38	0.46	0.60

Assumptions: (i) Survey response rates from the treatment and control groups are the same
(ii) Outcome variable is a continuous variable

Methods

Data

De-identified data will be extracted from the administrative and patient records. We will verify part of the administrative data, such as readmission rates, with a national database maintained by the Ministry of Health, that includes reportable readmissions data. We will also conduct a short survey to gauge patient and patient family satisfaction as another outcome measure.

We will use deidentified patient-related data from administrative databases of all public health institutions (PHIs) over the period Oct 2015 – Jun 2017. We sought and have obtained a waiver of informed consent for retrospective use of patients' administrative data. Our use of deidentified patient-related data from administrative databases from PHIs other than NUH has been approved by the Ministry of Health (MOH). We will collect additional data from patients and caregivers using surveys that we plan to carry out over the phone just after discharge, as well as one, two and six months after discharge. Each survey should take around 15 minutes. Consent for the follow surveys will be obtained as discharge.

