Data on patients' compliance behaviors will be obtained during their scheduled specialty outpatient clinic visits, including a pill count, and clinical indicators such as HbA1C, fasting lipids, blood pressure, height, weight, ambulatory status.

Outcome measures

Our primary measures are length of stay at readmission, number of readmissions within 90 days, number of visits to the specialty outpatients clinics, the number of emergency department visits (planned and unplanned) post-discharge, and patient satisfaction.

Statistical Analysis Plan

Inpatient and discharge data will come from the National University Hospital, Singapore. Other data on health service utilization outside the NUH system will come from the Ministry of Health omnibus dataset.

We will compare the outcome variables between the control (non-CareHub) and treatment (CareHub) groups using t-tests, Chi-square tests and hazard models depending on the variable type.

We will also control for any differences in baseline characteristics of patients (e.g. in comorbidities and types of healthcare interventions received) and caregivers in the control and treatment groups by regression analyses. We acknowledge that we will face the multiple comparisons problem (i.e. as more outcomes are considered, it becomes increasingly likely that the control and treatment groups will differ on at least one outcome by random chance alone) by examining such many outcome variables.

We will consider the following methods to counteract the problem of multiple corrections: Bonferroni correction; comparing the number of outcomes with significant differences to the total number of outcomes examined; creating an index that combines certain outcome variables.

We will also be performing a cost-effectiveness analysis that compares the relationship between difference in costs and selected outcomes across the treatment and control groups. Examples of outcomes include number of readmissions or unplanned readmissions and quality adjusted life years.

All statistical analyses will be performed with Stata 13.0.

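### For the three primary utilisation counts, the plan does not prespecify adjustment for the patient's own prior utilisation, although the administrative extract already holds it

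*Combined protocol and SAP*

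**What the plan says.** The Outcome measures section lists five primary measures, and three are counts: readmissions (90-day window), specialty clinic visits (no period given) and "the number of emergency department visits (planned and unplanned) post-discharge" (no end point given).

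The Statistical Analysis Plan section compares the arms "using t-tests, Chi-square tests and hazard models depending on the variable type". It does not say which test goes with which outcome. It then adds regression to control for differences in baseline characteristics, with comorbidities and interventions received as examples. It gives no model family, no covariate list and no statement of whether the adjusted or the unadjusted result is the main one. Prior utilisation is not mentioned.

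The Data section describes an extract from "administrative databases of all public health institutions (PHIs) over the period Oct 2015" to June 2017. Recruitment runs from 20 April to the end of November 2016. The Sample size section plans that "250 will be enrolled in CareHub, with a corresponding 250 in the control group".

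**The concern.** Resource utilisation is the first outcome named in the Objectives, and the sample is limited to about 500 patients. A patient's earlier use of a service is usually a good predictor of later use. Here it is measured before randomisation and is available at no extra cost. If the main comparison leaves it out, precision is lost.

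The regression wording can be read as adjustment for whatever imbalance turns up. An analyst could then choose between adjusted and unadjusted results, and choose the covariates, after seeing the data. That sits badly with a plan that already acknowledges a multiplicity problem.

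A second, smaller matter is that clinic and emergency visits have no common window, while observable follow-up differs about two-fold between early and late recruits.

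**Working it through.** **Inputs from the documents.** Two-sided 5% error ("based on a 5% (2-sided) Type 1 error rate"); 250 per arm; equal allocation ("the number of patients in the Usual Care and CareHub groups will be equal"); the stated dates. Table 1 rests on the assumption "Outcome variable is a continuous variable".

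**Input that is assumed.** ρ, the correlation between a patient's pre-index and post-discharge counts. The documents give no correlation, SD or event rate for any utilisation outcome.

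**Step 1: reproduce Table 1.** MDE = (z₀.₉₇₅ + z_power) × √(2/n per arm), with SD = 1.

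| Responders | 80%: computed / stated | 90%: computed / stated |
|---|---|---|
| 400 | 0.280 / 0.28 | 0.324 / 0.32 |
| 300 | 0.324 / 0.32 | 0.374 / 0.38 |
| 200 | 0.396 / 0.40 | 0.458 / 0.46 |
| 120 | 0.512 / 0.52 | 0.592 / 0.60 |

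The table reproduces: power at every stated value is within 2 points of nominal. It assumes no covariate adjustment.

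**Step 2: administrative outcomes, unadjusted.** At 250 per arm and 80% power, MDE = 2.802 × √(2/250) = 0.251.

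**Step 3: adjust for the prior count.** The residual SD becomes √(1 − ρ²). Power at d = 0.251 is Φ(2.802/√(1 − ρ²) − 1.960). For ρ = 0.4 this is Φ(2.802/0.917 − 1.960) = Φ(1.097) = 86.4%.

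| ρ | Power | Gain (points) | Adjusted 80% MDE |
|---|---|---|---|
| 0.2 | 81.6% | 1.6 | 0.246 |
| 0.3 | 83.6% | 3.6 | 0.239 |
| 0.4 | 86.4% | 6.4 | 0.230 |
| 0.5 | 89.9% | 9.9 | 0.217 |
| 0.6 | 93.8% | 13.8 | 0.200 |

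From a 90% base (d = 0.290) the gain is smaller: 4.3 points at ρ = 0.4 and 8.2 at ρ = 0.6.

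**Step 4: simulated counts.** Gamma-Poisson counts, 250 per arm, 3,000 replicates, with the same patient frailty before and after the index admission. The t-test is set against linear regression on the 180-day prior count (entered raw and logged), plus follow-up time where it varies. Rates, frailty variances and rate ratios are assumed.

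| Outcome (yearly rate, frailty variance, rate ratio) | ρ | t-test | Adjusted |
|---|---|---|---|
| 90-day readmissions (1.0, 1.0, 0.55) | 0.26 | 74.1% | 77.0% |
| 90-day readmissions (1.5, 1.0, 0.60) | 0.33 | 74.8% | 79.3% |
| 90-day readmissions (2.0, 1.5, 0.60) | 0.50 | 79.2% | 87.3% |
| Emergency visits, 212–436 days (1.5, 1.0, 0.73) | 0.48 | 71.2% | 80.9% |
| Emergency visits, 212–436 days (2.0, 1.0, 0.74) | 0.55 | 72.3% | 85.9% |
| Clinic visits, 212–436 days (6.0, 0.5, 0.82) | 0.63 | 72.2% | 92.1% |

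The gains are 3 to 8 points for 90-day counts and 10 to 20 for open follow-up. They assume fully stable patient risk, so they are optimistic. With risk stable in only half of patients, simulation at a rate ratio of 0.65 gave about 1 to 4 points.

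**Step 5: where the gain comes from.** In simulations at a rate ratio of 0.65, the t-test and an unadjusted negative binomial model had the same power with equal 90-day follow-up (52–56% each). With open follow-up, the count model with exposure time gave 80–84% against 78–83%. Exposure therefore adds 1 to 2 points, and the prior count supplies nearly all the rest. Type I error stayed near 5%.

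**Step 6: is the history there?** From 1 October 2015 to 20 April 2016 is 202 days; to 30 November 2016 it is 426. A 180-day look-back leaves 202 − 180 = 22 days to spare for the first patient, so it is complete for everyone only if the extract starts by about 23 October 2015.

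**Step 7: follow-up.** From enrolment to 30 June 2017 is 436 days for the first recruit and 212 for the last, a ratio of 2.1. Counting from discharge shortens both a little.

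**The case against.** A reader might infer that the plan commits the counts to t-tests and ignores history. The text does not say that. The choice of test depends on variable type, none is tied to an outcome, and regression is planned with an open list of examples. Prior utilisation is unspecified, not excluded. This objection stands, and it limits the point to a missing prespecification.

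A reader might also infer that unequal follow-up biases the comparison. Readmissions already have a fixed 90-day window, which falls inside the extract for all recruits unless an index stay is exceptionally long. For the other two counts, randomisation should balance calendar follow-up between arms, so the spread mainly adds noise. Bias would need death or loss to differ by arm.

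Nor do the figures show that a negative binomial model is required. In simulations at a rate ratio of 0.65, linear adjustment reached 59–69% power at 90 days and 92–97% with open follow-up; the adjusted negative binomial reached 59–66% and 90–93%. The t-test on raw counts is itself valid at this sample size.

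Finally, stable risk is doubtful in patients recruited on post-cardiac-surgery wards and selected by a risk score, because the index event may change their pattern of use. That is a fair reason to expect the lower part of the range, especially for sparse 90-day readmissions.

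What the objections leave standing is that the main analysis, the covariate and two of the three count windows are not fixed, and that a useful covariate already held is not named.

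**Conclusion.** The point holds as a recommendation to prespecify an adjusted main analysis. The plan's unadjusted comparison is not invalid; it is less precise than it could be. From an 80% base at 250 per arm, the gain is 1.6 to 3.6 points of power for a pre/post correlation of 0.2 to 0.3 and 6.4 to 13.8 points for 0.4 to 0.6. Nothing in the documents says where in that range the trial lies, so 6 to 14 points should not be quoted as an established loss. The day counts assume an extract running from 1 October 2015 to 30 June 2017. The missing window for clinic and emergency visits is a real gap in outcome definition, but its effect on power alone is small.

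**What to change.** For each of the three counts, make the main comparison a regression on arm and the patient's count of the same event in the 180 days before the index admission. Fit it whether or not the arms look imbalanced, with robust standard errors. Use a linear model for a difference in mean counts, or a negative binomial model if a rate ratio is wanted, and name the choice in advance. Keep the unadjusted t-test as a sensitivity analysis.

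Count clinic and emergency visits over one fixed post-discharge window that every patient can complete before the extract ends, or include available follow-up time in the model. Use an offset for days alive only as a sensitivity analysis: if mortality differs by arm, it changes the estimand from events per patient randomised to events per day alive.

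Confirm the first date of the extract, and shorten the look-back for all patients if it starts after about 23 October 2015.

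The cost is revised SAP wording and one derived variable per count from data already approved for use. The downside is slightly more model dependence, which the robust errors and the retained t-test limit.
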